4.0 Recruitment Methods

4.1 Identification of subjects

Patients who plan to remain in residential treatment for a minimum of 4 weeks at CaronTC will be identified. Patient records will be evaluated by Caron-based study staff against the study inclusion and exclusion criteria.

4.2 Recruitment process

4.2.1 How potential subjects will be recruited.

All eligible patients will be approached and recruited in the same manner following the study protocol procedures. Only IRB-approved study team members (Physicians or staff) at CaronTC will first interact with the patient in a consultation session. During the initial consultation session, the physician/staff will briefly explain the proposed study and ask the patient if they would be interested in discussing further with a research study member. If the patient is interested, a trained research study team member will discuss the full study including any risks and benefits associated with participation.

4.2.2 Where potential subjects will be recruited.

Potential subjects will be recruited on the Professionals Unit at CaronTC. Subjects may also be drawn from other units at the CaronTC if there is a planned stay of a minimum of 4 weeks.

4.2.3 When potential subjects will be recruited.

Potential subjects will be recruited prior to any study procedures taking place.

4.2.4 Describe the eligibility screening process and indicate whether the screening process will occur before or after obtaining informed consent. Screening begins when the investigator obtains information about or from a prospective participant in order to determine their eligibility. In some studies, these procedures may not take place unless HIPAA Authorization is obtained OR a waiver of HIPAA Authorization when applicable for the screening procedures is approved by the IRB.

Screening of subjects at admission is expected prior to obtaining consent to confirm that they have an established diagnosis of OUD.

Once informed consent is obtained, patients will undergo additional screening to determine if they are eligible to participate in the study based on the inclusion/exclusion criteria

5.0 Consent Process and Documentation

5.1

it Pro	cess and Documentation
Cons	ent Process:
Chec	k all applicable boxes below:
	nformed consent will be sought and documented with a written consent form [Complete Sections 5.2 and 5.6]
	mplied or verbal consent will be obtained – subjects will not sign a consent form (waiver of written documentation of consent) [Complete Sections 5.2, 5.3 and 5.6]
	nformed consent will be sought but some of the elements of informed consent will be omitted o altered (e.g., deception). [Complete section 5.2, 5.4 and 5.6]

☐ Informed consent will not be obtained – request to completely waive the informed consent
requirement. [Complete Section 5.5]

5.2 Obtaining Informed Consent

5.2.1 Timing and Location of Consent

An IRB-approved study team member will meet with the subject in a quiet private area. After careful and complete explanation of the study details, risks, and other options are provided to the subject, and a copy of the consent form will be provided to them for review. If they are interested in consenting to this study, they will be given additional time to ask questions. When all questions have be answered to their satisfaction by a study team member, the subject will be asked to sign the informed consent document.

5.2.2 Coercion or Undue Influence during Consent

During the initial consultation session, the IRB-approved physician/staff member will briefly explain the proposed study and ask the patient if they would be interested in discussing further with a research study member. If the patient is interested, a trained research study team member will discuss the full study including any risks and benefits associated with participation.

To ensure the consent process provides the patient with clear, accurate information, research staff involved in the consent process will undergo training to promote effective conversations as well as training on study-specific details.

Study team members will stress that participation is completely voluntary. Additionally, it will be carefully and clearly explained that if they should decide not to participate in this study, that decision will have no impact on the care the patient will receive.

Due to a conflict of interest by [name], informed consent for the study will be obtained by a non-conflicted, IRB-approved co-investigator or study coordinator, but he may be involved in the explanation of the protocol and its risks and benefits, answering patient questions, and in assuring that subjects meet the study entry criteria.

5.3 Waiver of Written Documentation of Consent

Not applicable

5.3.1 Indicate which of the following conditions applies to this research:

	The research presents no more that minimal risk of harm to subjects and involves no
	procedures for which written consent is normally required outside of the research context.
OR	
	The only record linking the subject and the research would be the consent document and the
	principal risk would be potential harm resulting from a breach of confidentiality. Each subject
	will be asked whether the subject wants documentation linking the subject with the research,
	and the subject's wishes will govern.
OR	
	If the subjects or legally authorized representatives are members of a distinct cultural group
	or community in which signing forms is not the norm, that the research presents no more
	than minimal risk of harm to subjects and provided there is an appropriate alternative
	mechanism for documenting that informed consent was obtained.

Describe the alternative mechanism for documenting that informed consent was obtained:

- 5.3.2 Indicate what materials, if any, will be used to inform potential subjects about the research (e.g., a letter accompanying a questionnaire, verbal script, implied consent form, or summary explanation of the research)
- 5.4 Informed consent will be sought but some of the elements of informed consent will be omitted or altered (e.g., deception).

Not applicable

- 5.4.1 Indicate the elements of informed consent to be omitted or altered
- 5.4.2 Indicate why the research could not practicably be carried out without the omission or alteration of consent elements
- 5.4.3 Describe why the research involves no more than minimal risk to subjects.
- 5.4.4 Describe why the alteration/omission will not adversely affect the rights and welfare of subjects.
- 5.4.5 If the research involves using identifiable private information or identifiable biospecimens, describe why the research could not be practicably be carried out without using such information or biospecimens in an identifiable format.
- 5.4.6 Debriefing
- 5.5 Informed consent will not be obtained request to completely waive the informed consent requirement

Not applicable

- 5.5.1 Indicate why the research could not practicably be carried out without the waiver of consent
- 5.5.2 Describe why the research involves no more than minimal risk to subjects.
- 5.5.3 Describe why the alteration/omission will not adversely affect the rights and welfare of subjects.
- 5.5.4 If the research involves using identifiable private information or identifiable biospecimens, describe why the research could not be practicably be carried out without using such information or biospecimens in an identifiable format.
- 5.5.5 Additional pertinent information after participation
- 5.6 Consent Other Considerations
 - 5.6.1 Non-English-Speaking Subjects
 Not applicable
 - 5.6.2 Cognitively Impaired Adults

Not applicable

- 5.6.2.1 Capability of Providing Consent
- 5.6.2.2 Adults Unable to Consent
- 5.6.2.3 Assent of Adults Unable to Consent
- 5.6.3.1 Parental Permission
- 5.6.3.2 Assent of subjects who are not yet adults
- 6.0 HIPAA Research Authorization and/or Waiver or Alteration of Authorization
 - 6.1 Authorization and/or Waiver or Alteration of Authorization for the Uses and Disclosures of PHI

Check	all that apply:
	Not applicable, no identifiable protected health information (PHI) is accessed, used or
	disclosed in this study. [Mark all parts of sections 6.2 and 6.3 as not applicable]

only box checked, mark sections 6.2 and 6.3 as not applicable]
Partial waiver is requested for recruitment purposes only (Check this box if patients' medical records will be accessed to determine eligibility before consent/authorization has been obtained). [Complete all parts of sections 6.2 and 6.3]
Full waiver is requested for entire research study (e.g., medical record review studies). [Complete all parts of sections 6.2 and 6.3]
Alteration is requested to waive requirement for written documentation of authorization (verbal authorization will be obtained). [Complete all parts of sections 6.2 and 6.3]

6.2 Waiver or Alteration of Authorization for the Uses and Disclosures of PHI

- 6.2.1 Access, use or disclosure of PHI representing no more than a minimal risk to the privacy of the individual
 - 6.2.1.1 Plan to protect PHI from improper use or disclosure
 Information is included in the "Confidentiality, Privacy and Data
 Management" section of this protocol.
 - 6.2.1.2 Plan to destroy identifiers or a justification for retaining identifiers

 Minimal screening activities prior to consent may include accessing patient
 charts to confirm eligibility. No identifiers will be retained for any patient
 who does not meet eligibility requirements to participate in the study.
- 6.2.2 Explanation for why the research could not practicably be conducted without access to and use of PHI

Information must be obtained from the subject's electronic medical record at Caron during recruitment to determine eligibility and, in some cases, to confirm information discussed with the subject in regard to their medical history.

6.2.3 Explanation for why the research could not practicably be conducted without the waiver or alteration of authorization

The waiver is requested only for recruitment to determine subject eligibility to ensure that no medical conditions that fall into the exclusion criteria are present and would thus preclude enrollment. This waiver will minimize the enrollment of subjects who may ultimately fail to meet the study inclusion/exclusion criteria.

6.3 Waiver or alteration of authorization statements of agreement

Protected health information obtained as part of this research will not be reused or disclosed to any other person or entity, except as required by law, for authorized oversight of the research study, or for other permitted uses and disclosures according to federal regulations.

The research team will collect only information essential to the study and in accord with the 'Minimum Necessary' standard (information reasonably necessary to accomplish the objectives of the research) per federal regulations.

Access to the information will be limited, to the greatest extent possible, within the research team. All disclosures or releases of identifiable information granted under this waiver will be accounted for and documented.

7.0 Study Design and Procedures

7.1 Study Design

Double-blinded, randomized, placebo-controlled pilot study to evaluate the effects of the GLP-1R agonist liraglutide treatment on drug craving in patients initiating residential treatment for OUD. In addition, the safety and feasibility of using GLP-1R agonist treatment in residential OUD patients will be established.

Study enrollment will not delay administration of standard of OUD therapies, such as behavioral treatments and/or buprenorphine/naloxone.

All participants, at the time of consent, will be enrolled in the 3-dose study procedure which takes 21 days to complete. As the vast majority of Caron patients remain in treatment for 28 days, the 3-dose procedure allows for the largest recruitment pool possible and provides a common procedure that all participants will complete. By Day 18 of the 3-dose procedure, participants will be asked whether they are able to, and willing to, continue the study for an additional 12 days (past Day 21) and receive 2 additional doses of the treatment medication (now considered the 5-dose study procedure). It is expected that not all participants will be willing or able to extend their study participation; additionally participants may either know their expected length of stay early (i.e., at admission to residential treatment) or not until close to completion of treatment. The decision to transition into the 5-dose procedure will be based on the participant's availability (i.e., whether the stay in treatment at Caron will be longer than the average 28 days) and on the participant's choice to extend their length of study participation.

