1.2 Primary Study Endpoints

The primary objectives of this pilot study are 1) to determine whether liraglutide can reduce cue-elicited drug craving over 3-5 weeks while participants are in residential treatment for OUD, and 2) to study whether liraglutide can reduce ambient (daily) drug craving over approximately 21-33 days while participants are in residential treatment for OUD.

- 1) Cue-elicited Drug Craving. Change in self-reported cue-elicited drug craving from baseline (Day 1) to the end of the target drug dose (Day 19 [and additionally until Day 31 for 5-dose intervention]) will be measured on a 0-100 point visual analog scale (VAS), where 0= no craving, 100= maximum craving. Assessments are taken prior to, and immediately after, exposure to visual drug cues in the Cue Response Task.
- 2) Ambient Drug Craving. Change in ambient drug craving over time will be measured throughout the study (Days 1-21 [and additionally until Day 33 for 5-dose intervention]) using a 0-100 VAS delivered via smartphone using Ecological Momentary Assessment (EMA) 4 times per day, on each test day (Days 1 and 19 [and additionally Day 31 for the 5-dose intervention]) and on the first two days and last 2 days of each treatment dose.

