fNIRs data files will be placed into the REDCap database, with access to these files provided to key investigators at Drexel University for signal processing and return for data analyses. These data will be de-identified and will consist only of the unique study id number, raw data, stimulus markers, and date/time stamps that have been modified so that they do not contain the actual visit date.

- **Study drug/placebo administration:** Participants will be taught self-administration by study/nursing staff.
 - All self-administrations will occur via blinded, multi-dose subcutaneous injection pens, and will be observed by nursing staff at CaronTC.
 - Participants will receive medications daily at a specified time (prior to breakfast) throughout the study, starting on Day 2.
 - Participants will be taught to inject the solutions subcutaneously in the abdomen, thigh, or upper arm, and will administer daily injections under the supervision of a study nurse or staff member.
 - Participants will be taught by study staff nurses to attach the needle, check the drug/vehicle flow, select the dose, inject the dose, remove the needle, and dispose of the needle.
 - o Participants will always use a new needle for each dose administration in the study.
- Adverse Events: Adverse events will be monitored continuously throughout the study (Days 1-21 [Days 1-33 for 5-dose intervention]), and at 30 days post-intervention (Day 49 [Day 61 for 5-dose intervention]).

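### Section 1.2 puts Day 31/33 data from self-selected extenders inside the primary endpoints, and Section 8.3 does not fix a primary time point common to all randomised participants

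*Combined protocol and SAP*

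**What the plan says.** Randomisation is 1:1 to liraglutide or placebo (Section 7.4.3). Length of treatment is not randomised. Under Section 7.1 all participants start in the 3-dose procedure, and "By Day 18 of the 3-dose procedure, participants will be asked whether they are able to, and willing to, continue the study". The basis is stated: "The decision to transition into the 5-dose procedure will be based on the participant's availability", meaning length of stay, "and on the participant's choice to extend their length of study participation". Uptake is expected to be partial, with no share given: "It is expected that not all participants will be willing or able to extend their study participation".

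Section 1.2 defines the first primary endpoint as change from Day 1 "to the end of the target drug dose (Day 19 [and additionally until Day 31 for 5-dose intervention" participants. The second, ambient craving by EMA, runs "throughout the study (Days 1-21 [and additionally until Day 33 for 5-dose intervention" participants.

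Section 8.3 plans an ANCOVA on baseline, a mixed model, and a 2×2 pre/post ANOVA for cue craving. None of them names the post-treatment day. For EMA it describes the primary analysis over roughly 21 days. Section 8.3 does not say how 3-dose and 5-dose participants are combined.

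Section 7.2.6 gives the two groups different conditions on Days 20-21: 3-dose participants are off drug in the rebound period, while 5-dose participants are on dose 4.

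**The concern.** Who contributes data after Day 19 is settled after randomisation, partly by willingness, and possibly after more than two weeks of blinded treatment. Section 10.0 lists nausea, diarrhoea and vomiting as common effects of the drug, so a choice that depends on arm is plausible. A choice that depends on craving is plausible too.

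Because the post-treatment day is not named, an analyst could use Day 19 in everyone, Day 31 in extenders, or each person's last dose. These are three different estimands, and the choice could be made with data in hand. Under Section 2.3 a trend towards efficacy here would support a multi-centre trial, so which of the three is primary matters.

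**Working it through.** **1. Timing.** Section 7.2 says "Participants will receive medications daily at a specified time (prior to breakfast) throughout the study, starting on Day 2". Day 2 to Day 18 inclusive is 18 − 2 + 1 = 17 dosing days. This is an upper limit, because some participants know their length of stay at admission.

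**2. The plan's own power.** Inputs from Section 8.2: n = 20 per group, d = 0.91, two-sided two-sample t-test, alpha 0.05, 20% attrition. With noncentrality δ = d·√(n/2) and 2n − 2 degrees of freedom:
- δ = 0.91 × √10 = 2.88 on 38 df gives power 80.1%. The effect detectable with 80% power is d = 0.91.
- 40/0.8 = 50 randomised.

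Both stated figures reproduce. They apply where all evaluable participants are measured, which for on-treatment cue craving is Day 19.

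**3. Power among extenders.** The share extending is not in the documents. Assuming equal shares in both arms:

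| Share extending | n per arm | Power at d = 0.91 | d for 80% power |
|---|---|---|---|
| 30% | 6 | 30% | 1.80 |
| 50% | 10 | 49% | 1.32 |
| 80% | 16 | 70% | 1.02 |

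For the middle row, δ = 0.91 × √5 = 2.03 on 18 df.

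**4. Bias from selection, with no true drug effect.** All inputs are assumptions: 20 per arm, SD 25, Day 19 to Day 31 correlation 0.7, about half extending, log-odds of extending 0.8 per SD of Day 19 craving. Results are for baseline-adjusted ANCOVA at Day 31 among extenders. The ranges reflect the assumed correlation with baseline.
- Choice unrelated to craving, or related equally in both arms: no bias, about 5% false positives (run at log-odds 1 and correlation 0.6).
- Only one arm's choice depends on craving: about 2-5 points, 6-8% false positives.
- Opposite directions by arm (stress case): about 4-11 points, 7-16%.

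The low ends correspond to a baseline correlation of 0.7. A weaker correlation moves the result towards the upper ends. Day 19 in all participants stayed unbiased, at about 5%.

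**5. Own-last-dose endpoint** (Day 31 if extended, otherwise Day 19). With log-odds 1 per SD and correlation 0.6, the bias runs against the drug. It is 0.09 SD (6.5% false positives) if lower craving favours extending in the liraglutide arm only, and 0.17 SD (9.9%) for opposite selection. Unequal uptake adds a second route: bias = (difference in extension rates) × (general fall in craving from Day 19 to Day 31). With 30% versus 60% extending and a fall of 0.25 to 0.5 SD, that is 0.3 × 0.25 = 0.08 SD to 0.3 × 0.5 = 0.15 SD.

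**6. EMA windows side by side.** Section 1.2 runs to Day 33 for extenders, while Section 8.3 says about 21 days. Cutting at Day 21 does not give a common condition, because Days 20-21 are off drug for one group and on dose 4 for the other (Section 7.2.6). Day 19 is the last day on which all participants follow the same schedule. The schedule footnotes list EMA on Days 1-3, 6-9, 12-15 and 18-21, so a Day 19 cut keeps 3 + 4 + 4 + 2 = 13 of 15 scheduled days.

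**The case against.** A Day 19 primary is the natural reading. Section 1.2 gives Day 19 for everyone and adds Day 31 as an extra, Section 7.1 calls the 3-dose procedure common to all, and the stated power matches Day 19. Section 8.3 does limit the EMA analysis to about 21 days. Length of stay is the first-named basis for extending and, when known at admission, cannot depend on arm. The trial is double-blind, and nothing in the documents suggests that selection would run in opposite directions by arm. This is also a pilot.

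The planned methods give some protection. In the step 4 setting with baseline correlation 0.7, a likelihood-type estimator using Days 1, 19 and 31 had bias of −0.15 points and 4.6% false positives, because selection on recorded craving is missing at random. The 2×2 ANOVA tests change scores, so its bias is near zero if baseline and Day 31 correlate equally with Day 19.

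Much of this stands, and it limits the size of the problem. It does not close the gap. The Day 19 reading is nowhere stated, and Section 1.2 places the later data in the primary endpoints. The mixed model cannot correct for unrecorded reasons for extending, and an ANCOVA restricted to extenders makes no use of the Day 19 information. The 21-day window still mixes conditions.

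A reader might infer that the primary comparison is itself non-randomised, or that false-positive rates near 19% with a spurious 12 points are to be expected. The documents support neither. Allocation stays randomised and blinded, and those figures need an unadjusted Day 31 t-test, which is not the planned analysis, together with opposite selection by arm.

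**Conclusion.** The point holds as an undefined primary time point combined with self-selected data written into the primary endpoints. The Day 19 comparison keeps its randomised basis and its 80% power at d = 0.91. A Day 31/33 or own-last-dose comparison is conditional on a post-randomisation choice and is underpowered: 49% at d = 0.91, with d = 1.32 needed for 80%, if half extend.

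Bias is possible, not established. For a Day 31 comparison among extenders it requires the choice to depend on craving differently by arm. The sizes (about 2-5 points, or 4-11 in the stress case, on a 0-100 scale) rest on the assumed uptake, SD, correlations and selection strength, none of which the documents give.

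**What to change.** In Sections 1.2 and 8.3:
- Name Day 19 (cue-elicited craving) and Days 1-19 (EMA) as the primary analysis for all randomised participants, whether or not they later extend. State that the post-treatment level in the ANCOVA and the 2×2 ANOVA is Day 19.
- Reconcile the 21-day and Day 33 EMA windows.
- Label Day 31/33 results exploratory. A mixed model using all visits may be reported alongside, with its missing-at-random assumption stated for the extension.
- Record and report extension rates and reasons by arm.

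The cost is wording plus one recorded item. Day 31/33 data no longer count towards the primary claim, and the primary EMA analysis gives up Days 20-21, which for 3-dose participants are already covered by the exploratory rebound endpoint in Section 1.4. No collected data are lost, the sample size stands, and no dosing rule changes.
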